### Inclusion Criteria:

- Women who present with symptoms of OAB, defined as a condition characterized by urgency, with or without urgency incontinence, usually with frequency and nocturia in the absence of obvious pathology or infection [9], with atrophic vaginitis.
- Postmenopausal:
  - by history, defined as twelve months or greater since last menstrual period
  - surgical menopause with removal of bilateral ovaries
  - age over 55 if they have had a previous hysterectomy alone without removal of bilateral ovaries.
- English language skills sufficient to complete questionnaires
- Clinical indication for vaginal estrogen use (hypoestrogenic findings on physical examination)
- Patients not currently receiving vaginal estrogen therapy

### Exclusion Criteria:

- Patients currently on systemic hormone replacement therapy (HRT) or who have been on HRT within the past three months
- Patients with current diagnosis or history of estrogen dependent malignancies (breast, endometrial)
- Contraindication or allergy to local estrogen therapy
- Insufficient language skills to complete study questionnaires
- Women with active, standard culture positive urinary tract infection at baseline assessment or Patients with a urine dip positive for leukocytes and nitrates on straight catheterized sample.
- Patients who have received antibiotics within the past two weeks
- Patients with stage 3 or 4 pelvic organ prolapse based on the pelvic organ prolapse quantitation system (POP-q)
- Patient unwilling to use vaginal estrogen preparation
- Patients currently on anticholinergic medication or who have received anticholinergic medication within the past three months

- Patients who have previously failed two medications for treatment of OAB or have previously received more advanced treatment for OAB including intra-vesicle botulinum toxin injections, posterior tibial nerve stimulation or implantation of sacral neuromodulator
- Patients wishing to start anticholinergic medication at the initial encounter
- Undiagnosed abnormal genital bleeding
- Active DVT, PE, or a history of these conditions
- Active arterial thromboembolic disease (for example, stroke and MI), or a history of these conditions
- Known liver dysfunction or disease
- Known protein C, protein S or antithrombin deficiency or other known thrombophilic disorders

### ***Patient Data Collection:***

**Visit 1 (baseline):** After enrollment and informed consent is obtained, patients will be asked to complete the OAB-q, a validated questionnaire, (**Appendix 3**) to measure OAB-related symptoms and quality of life [17]. Voided urines will be collected in a hat for 16SrRNA, PCR and protein analysis. A perineal swab will then be collected and assessed by 16S rRNA sequencing. Then a 30 mL vaginal lavage will be collected from the anterior wall of the vagina using sterile water for PCR and protein analysis. A vaginal swab will also be collected from the posterior fornix prior to the catheterized urine collection and assessed by 16S rRNA sequencing. Following the collection of the vaginal swab, a post void residual specimen will be collected by transurethral catheter, which is part of our standard practice for new patients. This specimen will be sent for standard clinical microbiology culture, EQUC and 16S rRNA gene evaluation. The specimens destined for the [name] lab will be stored on ice until pick up and transport. The swabs and urine for culture will be stored at room temperature until processed. The urine for sequencing will be refrigerated.

Demographic information and clinical characteristics will be collected, including age, parity, medical illness, previous hysterectomy, previous incontinence surgery, post void residual volume and body mass index (**Appendix 4**).

Physical examination will be completed, including evaluation for pelvic organ prolapse with the POP-q examination, which is part of a standard initial clinical evaluation.

Patients will be counseled on the evidence-based, first-line options for the treatment of OAB, including behavioral modifications, physical therapy, and vaginal estrogen per standard practice in our clinic. All study participants will be provided vaginal estrogen Premarin Cream® 0.625 mg conjugated estrogen/gram and instructed to use 0.5 grams twice weekly with the applicator. This is based on the clinical practice guidelines for vaginal estrogen use in postmenopausal women with urogynecological complaints developed by the Society of Gynecological Surgeons Systematic Review Group [18]. Patients will receive compensation at visit one with a parking voucher.

Patients will be given a medication diary for the use of vaginal estrogen to assess compliance (**Appendix 5**).

**Visit 2 (12 weeks):** Patients will be scheduled to return at twelve weeks from the initial visit for follow up which is part of our standard practice. They will be called a few days prior to the scheduled appointment as a reminder of the appointment and reminder to bring the medication diary. At the follow up, patients will repeat the OAB-q to reassess symptoms and quality of life measures. Again, voided and transurethral catheterized urine samples will be collected for analysis as described in visit 1. The perineal swab, vaginal lavage sample, and vaginal swab samples will also be collected at this visit and processed as described in visit 1. The patient will be screened for vaginal bleeding or spotting. The patient will be compensated with a second parking voucher at the conclusion of the study participation.

At this point, based on the patients' response to treatment, they may continue using vaginal estrogen. The symptoms of OAB will be reassessed and the next step in treatment will be based on the clinician's usual practice.

**Adverse Event Reporting:** We do not anticipate adverse events with this protocol; however as with all clinical protocols, it is feasible that a variety of unforeseen adverse events could occur. The risk of serious adverse event from the study participation in this protocol is extremely low and could include allergic reaction to the estrogen preparations, which would be considered reportable.

We would also report privacy breaches. There is also an unlikely risk of privacy violation despite diligent adherence to protection of all identified human data, using the Loyola secure server and in compliance with our institutional policies.

**Sample Collection and Preparation:** Consenting participants will contribute 2 catheterized urine samples and two voided urine samples: at the first visit and 12 weeks later. Urine samples obtained at the first visit are part of routine standard care and thus will be sent to the Clinical Microbiology Lab for standard urine culture. The Clinical Microbiology Lab also will assess the catheterized urine sample by EQUC. The Genomics Facility will perform 16S rRNA gene sequencing on the voided and catheterized urine samples and the [name] lab will do PCR and protein analysis. Both urine samples obtained at 12 weeks will be assessed by 16S rRNA gene sequencing, PCR and protein analysis. Catheterized urine samples will also be assessed by EQUC.

Immediately after collection, the human subjects-certified research team personnel will refrigerate and de-identify each urine sample, removing all protected health information prior to submission to any non-clinical investigators. Only the study ID will be available to individuals who are not involved in human subject recruitment, retention and oversight. Within 4 hrs, 1 aliquot of the catheterized urine sample will be sent to the clinical microbiology lab for standard culture and EQUC. A 2nd aliquot of the voided and catheterized urine sample will be sent to the genomics facility, where it will be inventoried and maintained in 10% DNA preservative (e.g., AssayAssure) at -80°C until bacterial DNA isolation and sequence analysis. After these analyses, leftover samples will remain stored in this biorepository for potential future IRB-approved analyses. A 3rd set of samples will be sent to the [name] lab for analysis of candidate AMPs (e.g. RNase 7, cathelicidin,  $\beta$ -defensins, s100A7) in urinary, vaginal and perineal epithelial cells (obtained from urine and vaginal lavage) and perineal/vaginal swabs.

**Sequencing:** Genomic DNA (gDNA) will be extracted from urine with the Qiagen DNeasy Blood and Tissue kit as described previously. We will amplify the V4 region of 16S rRNA, add Illumina sequencing adapters and dual-index barcodes, purify the resulting amplicons, quantify, and sequence using the Illumina MiSeq System. To assess potential DNA contamination, an extraction (no urine) negative control will be processed with the samples and sequenced in every run. To ensure reproducibility, each sample will be independently extracted and sequenced at least twice. This is the protocol used for our recent publications [1, 2].

**Bioinformatics Analysis:** Quality control and de-multiplexing of sequence data are done with onboard MiSeq Control software and MiSeq Reporter (current version: 2.1.43). The *mothur* pipeline, specifically formatted for its use with MiSeq-generated data will combine paired end reads and remove contigs of incorrect length (<285 bp, >300 bp), contigs containing ambiguous bases and chimeric sequences. Within *mothur*, sequences will be assigned to OTUs and taxonomically classified using a naïve Bayesian classifier and the *mothur*-customized RDP training set v9. Alpha diversity metrics (inverse Simpson index, Shannon index), beta diversity metrics (PCoA plots), mean sequence abundance, and dendrograms will be generated using *mothur*, METAGENassist and R. This protocol was used for our recent publications [1, 2].

**Standard and Expanded Urinary Quantitative Culture (EQUC) Procedures:** Catheterized urine samples are processed with standard and/or EQUC methods. Standard urine culture involves inoculation of 0.001 mL of urine onto 5% sheep blood agar plate (BAP) and MacConkey agar plate, incubated aerobically at 35°C for 24h. Thus, the level of detection for standard culture is 10^3 CFU/mL, represented by 1 colony of growth on either plate. In contrast, EQUC involves inoculation of 100X (0.1mL) more urine onto diverse types of media (BAP, chocolate agar, colistin and nalidixic acid (CNA) agar, CDC anaerobe 5% BAP) with incubation in more environments and temperatures (5% CO2 at 35°C for 48 h, aerobic conditions at 35°C & 30°C for 48 h, Campy gas mixture (5% O2, 10% CO2, 85% N) or anaerobic conditions at 35°C for 48 h). The level of detection for EQUC is 10 CFU/mL, represented by 1 colony of growth on any plate. Each morphologically distinct colony type in both standard and EQUC procedures will be counted and isolated on a different plate of the same media to prepare a pure culture to be used for identification with Matrix-Assisted Laser Desorption/Ionization Time-of Flight (MALDI-TOF) mass spectroscopy. This is the protocol used for our recent publications [1, 2].

**Biolog Assay:** Characterization of bacterial strains isolated from urine obtained from the female bladder by transurethral catheter will facilitate our understanding of the role that these bacteria play in the bladder. For

example, commensal bacteria of the gut are known to inhibit the growth of pathogenic bacteria by outcompeting the pathogen for available nutrients, a process called colonization resistance.

The Biolog assay is de rigeur for determining bacterial growth characteristics. It requires a device that the Loyola team does not possess, but Kimberly-Clark does. Thus, the isolates will be sent to Kimberly-Clark for Biolog characterization.

The urinary bacterial isolates received by Kimberly-Clark will be undergo phenotypic analysis of their growth curves and biochemical utilization profiles. To determine growth rates isolates will be grown in a nutrient rich broth and a nutrient limited broth. Bacterial growth will be measured kinetically using a spectrophotometer under the appropriate atmospheric conditions. Biochemical utilization profiles of the isolates will be determined using a series of Biolog plates, either endpoint or kinetic growth will be measured.

**Data Storage and Confidentiality:** Following HIPPA guidelines, patient identifiable data will be coded to protect each patient's identity. The data obtained from the patients will be entered onto electronic forms in the secure Redcap database. We are familiar with using this technology from other studies. It is efficient to complete in a clinical setting and minimizes data entry errors. The data will be presented in peer reviewed manuscripts and other public presentations at the group level only. No individual patients will be identified.

**Statistical Analysis Plan:** All data will be maintained on the Loyola secure, HIPAA-compliant research server. Only human-subjects certified team members will have access to identified data. Laboratory assessment will be performed using anonymized data and unique study numbers for each subject.

Statistical analyses of the microbiome data (EQUC and 16S rRNA) will be performed using SAS software version 9.4. Descriptive statistics for demographics, clinical characteristics, and microbiome data will be calculated including means with standard deviations, medians with interquartile ranges, or counts and percentages. Medians and interquartile ranges will be presented for OAB-q subscales at each time point as well as a change score, and Wilcoxon signed-rank tests assessed statistical significance of change in OAB-q. Each diversity measure will be modeled as a separate dependent variable in a linear mixed-effects regression, with independent variables including time, OAB-q symptom severity, physical therapy completed, weeks of estrogen compliance, and body mass index, and random intercepts for subjects. Spearman's rho will be calculated for change in Lactobacillus levels associated with change in the OAB-q symptom severity (12-week minus baseline values). For AMP data analyses, Spearman's rho will be used to test associations between change in relative abundance and change in area of bacterial growth inhibition.

**Expectations:** Since the FUM is more diverse in women with UII than in women without UII, since the bacteria of the FUM are similar to those of the vagina, and since estrogen treatment can reverse the increased diversity of the vaginal microbiome associated with menopause, we predict that estrogen treatment will make the FUM less diverse and improve LUTS. On the basis of our recently published study [1], we expect that hypoestrogenic women with UII, on average, will have 3 different bacterial species as detected by EQUC. We predict that estrogen treatment will reduce this average number towards the average of 1 bacterial species as detected by EQUC in the continent controls from our previous study [1]. In that study, the difference between women with UII and women without UII was highly significant ( $p=0.0001$ ). In the proposed study, we anticipate a smaller difference (since all women will have UII) and will consider significance at  $p<0.05$ . Since 16S sequencing and EQUC provide complementary views of the FUM [1], we anticipate that sequencing will provide similar results; however, sequencing can identify bacteria that are not cultured, even by EQUC, and thus will provide us with a broader view of FUM composition. We predict that AMP levels will correlate with certain microbiota profiles, and anticipate that increased AMPs *via* estrogen supplementation will correlate with improved frequency and severity of OAB symptoms.

**Possible Limitations to the study:** We do not anticipate any problems recruiting and retaining patients, as we have a long track record of similar studies. We anticipate some loss to follow-up (~7%). The timing of the first sample, taken at the first visit, will be necessarily variable but will be about 12 weeks from the commencement of estrogen treatment.

We do not anticipate any problems in the transfer of samples from the Ambulatory Clinic to the Clinical Microbiology Lab or the Genomics Facility, respectively, for culture and sequencing, as we have an established

and successful protocol for such transfer. For similar reasons, we also do not anticipate problems with the culture or sequence analyses.

We know that some urinary bacteria do not grow, even under EQUIC conditions. We also know that some bacteria are not readily sequenced. However, the strengths and weaknesses of EQUIC and sequencing are complementary and thus permit a broad and relatively unbiased view of the bacterial composition of the FUM.

The study will also exclude patients with severe urgency urinary incontinence as mentioned in the exclusion criteria. We reasoned that these patients might benefit from an anticholinergic medication prescribed at visit one. There is some evidence from our unpublished data that anticholinergic medications affect the FUM, making estrogen's effect on the FUM less clear if given concomitantly. These patients may represent a unique FUM that will not be studied in this project. In future studies, we plan to include patients with severe UUI receiving anticholinergic medications along with estrogen.

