While almost nothing is known about urinary/vaginal microbiome interplay, even less is known about immune response modulation in the bladder and vagina. However, estrogen reduces the subsequent UTI rate in hypoestrogenic women affected by recurrent UTI [9, 10], and estrogen induces urothelial antimicrobial peptide (AMP) expression [15]. Since AMPs exhibit microbicidal activity, stimulate inflammation, and facilitate epithelial barrier homeostasis [11], estrogen may work through AMPs as mediators to optimize microbial equilibrium.

**We hypothesize that, following estrogen treatment of hypoestrogenic women with OAB, symptom improvement will be associated with 1) reduced FUM diversity, 2) alteration of other FUM characteristics and 3) increased AMP levels.** We propose two specific aims:

**Aim 1: To compare pelvic floor microbiome (PFM) diversity and AMP levels before and after estrogen treatment in hypoestrogenic women with OAB symptoms.**

We will enroll 20 hypoestrogenic patients with bothersome OAB prior to clinically indicated vaginal estrogen treatment as part of a pilot study. We will collect catheterized urine, voided urine, perineal swabs, vaginal swabs and vaginal lavage at baseline and 12 weeks post treatment. We will assess the associated PFMs (i.e. urinary and vaginal microbiomes) using two complementary approaches: (i) Expanded Quantitative Urine Culturing (EQUC) and/or (ii) 16S rRNA amplicon sequencing. We will quantify candidate AMPs by quantitative PCR and protein analysis [12, 13]. We will compare and contrast each PFM and its associated AMP profiles. Relevant questions include: Do associations exist amongst adjacent PFMs and between PFMs and AMPs? Do PFMs and AMPs change in response to estrogen? Does an improved (less diverse) PFM correlate with an optimized AMP profile?

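### A vaginal lavage listed before the catheterized urine could carry vaginal bacteria into the bladder specimen, and the collection order is not fixed for both visits

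*Combined protocol and SAP*

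**What the plan says.** The Visit 1 (baseline) paragraph mentions the specimens in this order: voided urine, perineal swab, vaginal lavage, vaginal swab, catheterized urine. The last three are introduced as follows:

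- Lavage: "Then a 30 mL vaginal lavage will be collected from the anterior wall of the vagina using sterile water".
- Vaginal swab: "A vaginal swab will also be collected from the posterior fornix prior to the catheterized urine collection".
- Catheterized urine: "Following the collection of the vaginal swab, a post void residual specimen will be collected by transurethral catheter".

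The catheter specimen is the bladder sample: "This specimen will be sent for standard clinical microbiology culture, EQUC and 16S rRNA gene evaluation". For Visit 2 (12 weeks), the text first names the voided and catheterized urines and then adds: "The perineal swab, vaginal lavage sample, and vaginal swab samples will also be collected at this visit and processed as described in visit 1".

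The EQUC procedures section states: "The level of detection for EQUC is 10 CFU/mL, represented by 1 colony of growth on any plate". The Sequencing section gives the only contamination control described: "an extraction (no urine) negative control will be processed with the samples and sequenced in every run". Among the Aim 1 questions is: "Do associations exist amongst adjacent PFMs and between PFMs and AMPs".

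**The concern.** Followed as listed, Visit 1 has staff rinse the vagina with 30 mL of water and then pass a catheter through the adjacent urethra. Any rinse fluid that reaches the catheter or the urine puts vaginal organisms into the sample that represents the bladder.

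Two conclusions are exposed. The first is the between-site question in Aim 1, because carry-over creates the association being looked for. The second is the response to estrogen. The background sections expect the vaginal community to be diverse in hypoestrogenic women and less diverse after treatment. If part of it is carried into the urine, bladder diversity could appear to fall when only the vagina has changed. That error would favour the study's hypothesis. Each woman is her own control, so no untreated group would expose it.

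**Working it through.** **Step 1: what order is actually fixed?**

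- Visit 1, lavage against perineal swab: the lavage sentence places the lavage next in sequence.
- Visit 1, vaginal swab against catheter: stated twice, swab first.
- Visit 1, lavage against vaginal swab: not stated. It follows only from the order of the sentences.
- Visit 1, lavage against catheter: not stated. It follows only from the order of the sentences.
- Visit 2: the catheterized urine is named before the lavage and swabs. The reference back to Visit 1 attaches to analysis and processing, not expressly to the sequence of collection.

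If order of mention is order of collection, the lavage precedes the catheter at baseline and follows it at 12 weeks. If order of mention means nothing, staff have no fixed sequence for the lavage at either visit. Neither reading guarantees the same conditions at both visits.

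**Step 2: would the planned controls detect carry-over?** The extraction blank contains no urine and enters at the laboratory, so it sees reagent and extraction contamination only. Duplicate extraction and sequencing would reproduce a contaminated urine faithfully. No collection-level control is described.

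**Step 3: direction of the effect on similarity.** Let v be the vaginal profile, b the true bladder profile (both as proportions), and f the share of the urine profile that comes from the vagina. Bray-Curtis dissimilarity is half the sum of absolute differences, so

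BC(v, (1−f)b + fv) = (1−f) × BC(v, b).

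With f = 0.05, 0.10 and 0.20, the observed dissimilarity is 0.95, 0.90 and 0.80 of the true value. These values of f are illustrations. The identity assumes that what is carried over has the same profile as the swab. If its profile is w instead, the dissimilarity is at most (1−f)BC(v, b) + f·BC(v, w), which is still below BC(v, b) whenever w resembles the swab more than the bladder does.

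**Step 4: does it cancel within a woman?** Let carry-over add c0 species to the urine at baseline and c1 at 12 weeks, with the bladder unchanged. The apparent change is c1 − c0. It is zero only if c0 = c1. A vaginal community that loses species on estrogen, or a lavage that precedes the catheter only at baseline, would tend to make c0 > c1, which looks like a fall in bladder diversity. For scale, Expectations predicts a move from 3 species towards 1. A net difference of one species would be 1/(3−1) = half of that full shift. This is a conditional statement, not an estimate.

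**Step 5: can a size be given?** The plan's limit reproduces: 1 colony / 0.1 mL = 10 CFU/mL. The volume of lavage fluid needed to reach it is

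volume (µL) = 10 CFU/mL × urine volume (mL) / lavage load (CFU/mL) × 1000.

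Lavage load and urine volume are not in the documents. Assuming 10^4 to 10^6 CFU/mL and 10 to 100 mL:

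- lowest: 10 × 10 / 10^6 × 1000 = 0.1 µL
- middle: 10 × 50 / 10^5 × 1000 = 5 µL
- highest: 10 × 100 / 10^4 × 1000 = 100 µL

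The range is a thousandfold. It shows that small volumes could matter, not that they are transferred. It also does not isolate the effect of order, since some vaginal fluid could reach a catheter with no lavage at all.

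**The case against.** The strongest reply is that the sequence is partly inferred. That is correct: no sentence orders the lavage against the swab or the catheter. It turns the point into a request to state the order but does not remove it, because the natural reading of Visit 1 puts the lavage first.

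A second reply is that within-patient analysis cancels a stable contaminant. The Statistical Analysis Plan uses random intercepts for subjects and change scores, so a constant amount would partly cancel. This contaminant is not expected to be constant (Step 4). The Statistical Analysis Plan also specifies no between-site test, which limits the reach into its named analyses, but the Aim 1 question remains.

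Third, the lavage water dilutes whatever is carried, catheterization is standard practice in this clinic, and silence on how the urethral opening is prepared does not show that nothing is done. All of this stands, and it is why no frequency or amount is asserted.

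A reader might go further and infer that rinsing dilutes the vaginal swab and so inflates vagina-bladder similarity. The documents do not support that. The swab is read by 16S, and uniform dilution leaves relative abundances unchanged. The lavage is at the anterior wall and the swab at the posterior fornix. If low biomass let in a 20% background share, the direction would depend on that background: in simulation, similarity rose in 86% of cases when the background shared taxa with the sites and in 0% when it did not. An unrinsed vagina still gives the cleaner swab, and swabs also go for AMP analysis, where quantity matters.

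**Conclusion.** The concern holds as a preventable risk. The protocol lists the lavage before the bladder specimen at Visit 1, does not fix the order at Visit 2, and describes no control that could reveal carry-over at collection. If carry-over occurs, it pushes vagina-bladder similarity upward and can make a vaginal response to estrogen pass for a bladder response.

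No magnitude is claimed. A reader might infer that the bladder results will be contaminated, or contaminated to a stated degree; the documents give no carry-over volume, vaginal load or urine volume from which to say so. The conclusion rests on reading Visit 1 in its natural order and on the protocol's own expectation that the vaginal community changes with estrogen. It is a cheap improvement to the procedure, not a defect that invalidates the design.

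**What to change.** State one collection order and apply it at both visits: voided urine, perineal swab, vaginal swab, catheterized urine, lavage last. In the Visit 2 text, say that the order of collection, not only the processing, follows Visit 1.

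This adds no specimen and no procedure; the cost is rewording. There is one possible downside. The lavage supplies epithelial cells for the AMP work and would now follow the swab and the catheterization, so the laboratory should confirm that this does not affect that specimen. If it does, take at least the vaginal swab before the lavage, and give the reason for keeping the lavage before the catheter.

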**Aim 2: Determine if FUM characteristics correlate with OAB symptoms.**

At baseline and 12 weeks, we will use the overactive bladder questionnaire (OAB-q) [14] to evaluate symptoms and determine if PFM characteristics (e.g., composition, diversity, abundance, specific organisms) and AMP levels (gene expression and protein levels) correlate with patient symptoms. Relevant questions include: Does response to estrogen associate with pre-treatment PFM and/or AMP characteristics? Do PFM and/or AMP changes correlate with treatment response?

**Significance:** The medical field is beginning to adopt treatments that alter an individual's microbiome and AMP profile to improve patient health; however, this approach has not been adopted for LUTS treatment. Here, we propose the first step in development of such a therapy. If our hypothesis is correct, we could validate estrogens a first line of treatment in hypoestrogenic women. It could also propel the use of an individual's PFM and/or AMP characteristics to develop future personalized therapies to improve treatment response and/or prevent LUTS.

[figure not shown]
**Estrogen improves OAB symptoms:** There is compelling evidence to suggest that vaginal estrogen therapy relieves symptoms of OAB including frequency, urgency and UUI in postmenopausal women [7, 8, 11, 12]. The evidence is sufficient to list the application of vaginal estrogen alone as a treatment option for OAB in the clinical practice guidelines for postmenopausal women with urogynecological complaints [18]. The mechanism of vaginal estrogen's effect on OAB symptoms is poorly understood. Vaginal estrogen has the ability to modify the vaginal microbiome and reduce recurrent urinary tract infections in postmenopausal women [16]. We reason that vaginally applied estrogen would also modify the FUM, which appears to play a role in OAB [1].

**The Bladder is Not Sterile.** Current treatments and preventive strategies are based upon the dogma that the bladder is a sterile environment. Compelling new evidence challenges this long-held belief. Detection of bacterial DNA and isolation of live bacteria from urine taken directly from the bladders of women with and without urinary symptoms has been reported by us [1-3], and by others [4, 5]. However, the role of the female urinary microbiome (FUM) in urinary health and disease is incompletely understood.

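### AMP protein is compared across visits in urine and lavage with no measured denominator for dilution or recovery, and the plan has no before-after AMP test to attach one to

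*Combined protocol and SAP*

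**What the plan says.** The third part of the hypothesis in Specific Aims is "3) increased AMP levels" alongside symptom improvement, and Aim 1 is "To compare pelvic floor microbiome (PFM) diversity and AMP levels before and after estrogen treatment in hypoestrogenic women with OAB symptoms". Aim 2 asks whether "AMP levels (gene expression and protein levels) correlate with patient symptoms". The assay description is one sentence: "We will quantify candidate AMPs by quantitative PCR and protein analysis".

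The specimens are described under Patient Data Collection, Visit 1. For urine: "Voided urines will be collected in a hat for 16SrRNA, PCR and protein analysis". For the vagina: "a 30 mL vaginal lavage will be collected from the anterior wall of the vagina using sterile water for PCR and protein analysis". Visit 2 repeats the collection. Sample Collection and Preparation adds that "Both urine samples obtained at 12 weeks will be assessed by 16S rRNA gene sequencing, PCR and protein analysis". The same section then places the candidate AMPs in epithelial cells recovered from urine and lavage, and in swabs.

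The Statistical Analysis Plan gives AMP data one sentence: a Spearman correlation between change in relative abundance (not defined) and change in the area of growth inhibition. Under Recruitment, each woman is compared only with her own baseline.

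**The concern.** AMP protein per mL depends on how much AMP is present and on how dilute the specimen is. A urine sample taken at a clinic visit varies in concentration from day to day. A 30 mL water wash recovers an unknown amount of secretion and cells, and the protocol does not say whether 30 mL is the volume instilled or the volume recovered.

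No section lists creatinine, specific gravity, osmolality, total protein, cell count, recovered lavage volume, time of day or time since last void. These sections do set out assay by assay what each specimen is for, so the omission matters. A denominator that was not assayed cannot be supplied at the analysis stage.

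With no untreated arm, any systematic difference in dilution or recovery between visits falls entirely into the before-after contrast. If it also tracks symptoms, it enters the Aim 2 correlation. If it is random, it only adds noise, which still matters in a pilot meant to inform a larger study.

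**Working it through.** **1. Is there a figure to reproduce?** No. The only stated power (0.816 at 60 women) concerns microbiome diversity. The documents give no AMP variance, unit or expected change.

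**2. Can the AMP method be looked up?** Not from the reference list. Aim 1 cites references 12 and 13 for the AMP assays. By title, these are a trial of estradiol vaginal tablets for atrophic vaginitis and a paper on a myogenic basis for overactive bladder.

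**3. Which matrix is assayed?** Visits 1 and 2 send urine and lavage for protein analysis, which reads as fluid. Sample Collection and Preparation names epithelial cells from those fluids, plus swabs. Creatinine is a sensible denominator only for protein in the fluid phase of urine. Cell lysate needs total protein or a cell count. The plan provides neither.

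**4. How dilution enters.** For each woman, log(measured week 12 / baseline) = log(true AMP ratio) + log(g), where g is the ratio of urine concentration, or of recovery, between visits. Two illustrations with assumed volumes:
- Urine, constant AMP excretion, output falling from 2.0 to 1.5 L per day: g = 2.0/1.5 = 1.33. This uses daily output, whereas the specimen is a single void.
- Lavage, 0.5 mL of secretion recovered at baseline and 1.0 mL at week 12, added to 30 mL: g = (1.0/31.0)/(0.5/30.5) = 1.97.

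**5. Effect of a systematic shift on a paired test.**
- Inputs from the documents: 20 or 60 women, about 7% loss, significance at 0.05. Pairs: 20 × 0.93 = 18.6, taken as 18; 60 × 0.93 = 55.8, taken as 55.
- Assumed: two-sided Wilcoxon signed-rank test, normal log change with SD 0.5, 0.8 or 1.1, no true AMP change, 2,000 simulated studies per cell.

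Share of studies declaring a significant increase (SD 0.5 / 0.8 / 1.1):

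| g | 18 pairs | 55 pairs |
|---|---|---|
| 1 (no shift) | 2.0% / 1.6% / 2.2% | 2.8% / 2.5% / 2.2% |
| 1.25 | 41% / 19% / 12% | 89% / 53% / 31% |
| 1.5 | 89% / 51% / 30% | 100% / 95% / 76% |
| 2 | 100% / 92% / 72% | over 99% throughout |

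The nominal rate in one direction is 2.5%. A shift the other way (g below 1) would mask a real rise.

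**6. Effect on the symptom correlation.** Let dilution explain a share f of the variance of AMP change and correlate r with symptom change, with no other link. Spearman's test at 5% is then significant as follows (r = 0.3 / r = 0.5):

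| f | 18 pairs | 55 pairs |
|---|---|---|
| 0.3 | 10% / 19% | 21% / 46% |
| 0.5 | 13% / 28% | 30% / 73% |
| 0.7 | 15% / 38% | 41% / 86% |

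At r = 0 the rate stays at about 5%.

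**7. Effect of random dilution.** There is no bias, but the SD is inflated. If f = 0.5 and the SD of log change is 0.8, a perfect correction would leave 0.8 × √(1 − 0.5) = 0.57. A real correction would achieve less.

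**The case against.** The strongest reply is that the plan is silent on assay detail generally, so a normaliser may be part of the laboratory's method. That cannot be excluded. However, the specimen sections list every planned use, and the cited methods do not resolve it, so the denominator still has to be written down.

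A reader might infer that a false rise is likely because women are counselled at Visit 1 on first-line options "including behavioral modifications, physical therapy, and vaginal estrogen per standard practice in our clinic" and may drink less. The documents do not support that. Fluid advice or intake appears nowhere, and every volume above is assumed. Only a systematic or symptom-linked shift causes bias.

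A reader might also infer that AMP protein is definitely measured in two diluted fluids. The text on epithelial cells leaves this open, and hydration matters much less for cell lysate.

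Two further points stand. Quantitative PCR gives a partial check on AMP production and is largely protected if a reference gene is used, although none is named. And for lavage, more secretion from treated tissue may be a real treatment effect. In the 0.5 to 1.0 mL example, AMP recovered per wash about doubles while AMP per mg total protein would stay flat. Which of these is the AMP level is a choice of estimand, so total protein should not be imposed as the sole lead measure.

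**Conclusion.** The gap is real and inexpensive to close. As written, the study cannot separate a change in AMP protein from a change in urine concentration or lavage recovery, and it has no before-after AMP test in which a correction could be made.

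What can be claimed is limited: added noise for certain, and bias only if dilution or recovery shifts systematically or with symptoms. The percentages show how sensitive a paired analysis would be to such a shift. They are not estimates for this study, because the shift, its direction and the AMP variance are all assumed. The concern applies to protein; gene expression is less exposed.

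The recommendation is firmest for fluid-phase urinary protein, where creatinine is a standard denominator (assuming estrogen does not alter its excretion). For lavage and cell lysate the recommendation is to measure and show both versions, because total protein may itself respond to estrogen.

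**What to change.** - State the matrix, unit and denominator for each AMP measure: fluid or cell lysate for urine and lavage, and the reference gene for qPCR.
- Measure creatinine at both visits on the urine sent to the AMP laboratory. Analyse fluid-phase urinary AMP protein per mg creatinine, with raw concentrations as a sensitivity analysis.
- For lavage, record the recovered volume and measure total protein; for any cell-lysate protein, measure total protein. Report raw and total-protein-normalised values side by side, without making the ratio the only lead measure.
- Add to the Statistical Analysis Plan a paired before-after AMP test (for example Wilcoxon signed-rank, as already used for OAB-q) and the correlation of AMP change with OAB-q change, both on these measures. Define relative abundance in the existing AMP sentence.

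Cost: routine assays on samples already collected, assuming enough volume remains (the protocol gives no aliquot volumes for the AMP laboratory), plus a few lines of text. The denominators add some assay noise of their own. The decision has to be made before the aliquots are used up.
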